### **Measure AROM of Knee Extension with Rebee Wearable Sensor**

The participant will be sitting at the edge of plinth with knee flexed, the sensor position at the level of the Lateral malleolus, participant will be asked to extend the testing knee through the full ROM.

[figure not shown]

The Digital goniometer and rebee wearable sensor will be used for comparison of their validity for measuring knee joint flexion and extension ROM.

Rebee wearable sensor will be used as mentioned above and this procedures will repeated two times with one week interval between measurements to test its reliability. Researcher will records all the measurement.

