# CHAPTER I

## INTRODUCTION

Range of motion (ROM) of the joint is one of the factors that determine function of the musculoskeletal system. This parameter should be measured and recorded by a valid and reliable method (**Yaikwawongs et al., 2009**). It is considered to be an essential component of lower limb physical examination, which can be applied using various instruments such as goniometers and inclinometers (**Pourahmadi et al., 2017**).

Range of motion of the knee joint is one of the major factors determining the outcome after knee injuries. It is also an important measurement required by many knee scoring systems to determine the preoperative status and postoperative outcome (**Anouchi et al., 1996**). Measurements are used by physical therapists to quantify limitations of motion, used to decide an appropriate therapeutic interventions, and document the effectiveness of these interventions. The ideal measuring device should give reproducible valid and reliable data (**Yaikwawongs et al., 2009**).

Two-arm digital goniometer is still widely used in measuring uniaxial ROM of joint of extremity, there is high validity, intra rater and interrater reliability of the digital goniometer. It is considered valid and reliable tool that simplify physical therapists' work (**Svensson et al., 2019**).

The measurement of joint ROM is required an essential skill in the musculoskeletal assessments commonly performed by physiotherapists. The digital goniometer is the most commonly utilized clinical tool for measuring joint range of motion, the evolution of sensors technology and applications are easy to use, relatively inexpensive, and highly accessible (**Keogh et al., 2019**).

Rebee is a wearable motion sensor package of sensor with its own mobile application, which measures range of joint movement in different planes easily which the patient able to wear the sensor and move easily to measure ROM and record the measurement at the application software, that is facilitate the tele-measurement which the patients are supposed to put on the sensors and perform the actions themselves, or with assistance from physical therapist.

So this study will be conducted to test the criterion related validity and intrarater reliability of the rebee wearable sensor in measuring active knee joint ROM compared with digital goniometer measurement.

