## **Hypotheses**

It is hypothesized that:

1. Rebee wearable sensor will not be valid to measure active knee joint flexion ROM compared with digital goniometer measurement.
2. Rebee wearable sensor will not be valid to measure active knee joint extension ROM compared with digital goniometer measurement.
3. Rebee wearable sensor is not reliable to measure active knee joint flexion ROM.
4. Rebee wearable sensor is not reliable to measure active knee joint extension ROM.

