### **Participants**

40 normal participant will be assigned to one group, this number detected by G\*power 3.1 software (Universities, Dusseldorf, Germany) was used for calculation.

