### **Selection of Subjects**

The participant will be recruited from faculty, staff, and students of Pharos University, Egypt. Graduate Program in Physical Therapy after achieving the inclusion and exclusion criteria. Each participant will sign an informed consent before beginning of the study to insure complete satisfaction (Appendix 1)

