### **Inclusion Criteria**

1. 40 normal participant's age ranged from 35 to 45. (**Miranda et al., 2002**)
2. The participant from both sex. (**Correll et al., 2018**)
3. Participant Body mass index (BMI) from (19 to 25) normal weight ( $BMI = \text{weight (kg)} / [\text{height (m)}]^2$ ) (**Weisell et al., 2002**).

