## Measure AROM of Knee Extension with Digital Goniometer

The participant will be at supine position with the testing knee flexed, which allows assessment of the joint ROM without interference from tightness in the rectus femoris muscle, axis location at lateral epicondyle of the femur, stationary arm will be along the femur to the greater trochanter, The movement arm will be along the fibula to lateral malleolus.

The participant will be asked to extend the testing knee fully through available ROM and the therapist will record the measurement to compare with rebebe wearable sensor measurement.

The following picture illustrates that measurement with the digital goniometer will be from the similar supine position of measurement with the conventional goniometer.

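### Extension validity and reliability (hypotheses 2 and 4) would be judged by Pearson's r, which depends on how much normal knees differ as well as on sensor error, and the recorded extension value is not defined

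*Combined protocol and SAP*

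**What the plan says.** Hypotheses treats extension separately from flexion. Hypothesis 2 reads "Rebee wearable sensor will not be valid to measure active knee joint extension ROM compared with digital goniometer measurement", and hypothesis 4 makes the matching statement for reliability.

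Participants states that "40 normal participant will be assigned to one group". Inclusion Criteria narrows this to "40 normal participant's age ranged from 35 to 45" and "Participant Body mass index (BMI) from (19 to 25) normal weight". Selection of Subjects says that people enter "after achieving the inclusion and exclusion criteria", but no exclusion criteria are listed, so healthy knees rest on the word normal.

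With the goniometer the participant lies supine, starts with the knee flexed, and "The participant will be asked to extend the testing knee fully through available ROM". With the sensor the participant sits at the plinth edge, also starts flexed, and the instruction is "participant will be asked to extend the testing knee through the full ROM". Neither section fixes the start angle, sets an intermediate angle, or says whether the recorded number is the final angle or the excursion. Range of Motion in Chapter II describes ROM as an arc.

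Statistical Analysis names means, standard deviations and Pearson's r, for validity and reliability alike. It gives no value of r that would count as valid or reliable and no limit in degrees. No between-person SD for extension appears anywhere.

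**The concern.** Pearson's r compares true differences between people with measurement error. The same sensor, with the same error in degrees, gives a high r in a varied sample and a low r in a uniform one. This sample is restricted by health status, age and BMI, and every participant goes to the same point in the range, full extension. If the recorded value is the end angle and normal knees differ little there, a sound sensor could be labelled not valid or not reliable for extension. For the same reason, the r values for flexion and extension could not be compared if their true spreads differ.

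The undefined value adds to this. If an arc is recorded, part of the spread comes from where each person happened to start. That start is taken lying down for one device and sitting for the other.

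**Working it through.** **The plan's own figure.** The only figure is N = 40, credited to G\*Power 3.1 without inputs, so it can be neither reproduced nor refuted. Using n = ((z_alpha + z_power)/atanh r)² + 3, 40 participants fit, for example, r of about 0.43 against zero (two-sided 0.05, 80% power), since (1.960 + 0.842)/√37 = 0.461 and tanh 0.461 = 0.43. They also fit about 0.49 at 90% power. A test of r against zero does not establish agreement in any case.

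**Inputs.** n = 40 is from Participants. The true between-person SD (S) and the error SD per reading (e) are assumptions, because the documents give neither. Errors are taken as independent, equal for the two readings, and free of offset and scale error.

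**Expected r.** r = S²/(S² + e²). For S = 2 and e = 3, r = 4/(4 + 9) = 0.31. Its Fisher-z 95% interval at n = 40 is tanh(atanh 0.31 ± 1.96/√37), about 0.00 to 0.57. Power to show r above zero (two-sided 0.05) is Φ(atanh r × √37 − 1.96).

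| True SD S (degrees) | r, e = 2 | r, e = 3 | Power, e = 2 | Power, e = 3 |
|---|---|---|---|---|
| 1 | 1/5 = 0.20 | 1/10 = 0.10 | 23% | 9% |
| 2 | 4/8 = 0.50 | 4/13 = 0.31 | 92% | 49% |
| 3 | 9/13 = 0.69 | 9/18 = 0.50 | near 100% | 92% |
| 5 | 25/29 = 0.86 | 25/34 = 0.74 | near 100% | near 100% |
| 8 | 64/68 = 0.94 | 64/73 = 0.88 | near 100% | near 100% |

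Simulation at n = 40 gave mean r within 0.01 of these values. Within each r column the device is identical; only the sample's spread changes.

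**Differences in degrees.** The SD of the paired difference is e√2, which is 2.83 for e = 2 and 4.24 for e = 3. The 95% limits of agreement around the mean difference are ±1.96 × 2.83 = ±5.5 and ±1.96 × 4.24 = ±8.3 degrees. S does not enter, so these are the same in every row. The planned summaries already contain what is needed: the variance of the difference is SD₁² + SD₂² − 2r·SD₁·SD₂. For S = 2 and e = 3 that is 13 + 13 − 2 × 4 = 18, whose root is 4.24.

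**If the value is an arc.** Let the start angle have SD T, independent of the end angle. If both readings share the same start, r = (S² + T²)/(S² + T² + e²), which is higher than the end-angle value. If the two starts are unrelated, r = S²/(S² + T² + e²), which is lower. With supine and sitting starts and no fixed angle, the documents do not show which case applies. In either case r partly describes the starting posture.

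**The case against.** The strongest reply is that the damaging case is assumed. A reader might infer that extension is read only at its end position, that normal knees barely differ there, and that hypotheses 2 and 4 therefore cannot be answered. The documents do not support that. Both tasks start flexed and move through the range, and Chapter II describes ROM as an arc, so the end-angle reading is an inference. No SD is given. The nearest text, in Physical Examination of ROM, says only that normal reference values vary slightly with age and gender, which is not a between-person spread. Nothing shows that the age and BMI limits narrow extension. At a true SD of 5 degrees r is 0.86 to 0.74, and with an error SD of 1 degree it is 4/5 = 0.80 even at a true SD of 2. This stands, so the size can be stated only conditionally.

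A reader might also infer that the plan sets out to measure limited extension and then never tests it. The Introduction does say "Measurements are used by physical therapists to quantify limitations of motion", but it and Chapter II speak of limited motion in general, not of extension. Normal participants are a declared delimitation, and the hypotheses claim nothing about limited knees. Nor can one say that a proportional sensor error must stay hidden. If an arc is recorded, a 15% error over an assumed 90-degree excursion is 0.15 × 90 = 13.5 degrees and would show in the planned means.

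None of this rescues r as the basis for judgement. Its dependence on spread is a property of the statistic, and an ICC shares it. The undefined value and unfixed start angle are gaps under either reading.

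**Conclusion.** The point holds in conditional form. Hypotheses 2 and 4 would be judged on a statistic that depends on the sample's spread as well as on the sensor's error, in a restricted sample whose extension spread the plan does not give, and on a value that it does not define. With an error SD of 2 to 3 degrees, expected r runs from 0.20 to 0.10 at a true SD of 1 degree up to 0.94 to 0.88 at 8. If the end angle is recorded and normal knees differ by only 1 to 2 degrees, a low r would not show that the sensor is poor. If an arc is recorded, the start angle contributes to r by an unknown amount.

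These figures rest on equal, independent errors without offset or scale error, and on SDs that are all assumed. The result does not show that extension r will be low, or that the hypotheses are unanswerable. The plan should be changed before enrolment, because the main repair is to the analysis and uses readings already planned.

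**What to change.** 1. In the two extension procedures (goniometer and sensor), state whether the recorded value is the end angle or the arc. If it is an arc, fix the start angle. Use the same posture for both devices, so that their difference does not include a change of position.
2. In Statistical Analysis, judge hypothesis 2 on sensor-minus-goniometer differences (mean difference and 95% limits of agreement). Judge hypothesis 4 on visit-to-visit sensor differences (SEM or repeatability coefficient, in degrees). Compare each with a limit in degrees that the investigator sets and justifies before data collection. Report r only as descriptive.
3. State that the conclusion applies to healthy adults aged 35 to 45 with BMI 19 to 25 at full extension, and not to limited extension angles.

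The second and third changes need only analysis work and wording. The first needs a protocol edit and one agreed posture. None needs more participants.

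Optional: add a few held positions short of full extension, read by both devices in one shared posture and analysed as differences at each position. Do not pool r over positions, because the chosen spread would inflate it. The cost is a few more minutes per session. Held positions are also imposed and less natural than the active movement in the hypotheses, so this is a trade-off and not a requirement.

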### **Steps for Using Rebee Sensor Package**

- 1- Take the charging end of the charging cable and look for the charging port on the sensor.

[figure not shown]
2- Making sure the cable aligns with the port then connect the charger.

[figure not shown]
- 3- The USB end of the charging cable must be connected to a USB port / USB charger.
- 4- Check the sensor for a red LED light to know that it is successfully charging. The red LED will turn off once the device is fully charged.

5- Wearing the devise at the level of the Lateral malleolus with the sensor light facing Lateral malleolus.

[figure not shown]
6- Connecting the sensor to the device

[figure not shown]
Step a: Switch on the sensor device.

Step b: Go to phone's settings and turn on device's Bluetooth.

7- Look for “HC-06” (Default sensor name) under “Available devices” and tap on it.

8- Identifying the Sensors to Software

Step a: Connect the sensor you are trying to identify  
 Step b: Look for the sensor in the list with the name “HC-06”

## **Statistical Analysis**

Statistical methods will be used to calculate the reliability and validity of our measurements will be descriptive statistics for mean and standard deviation, also the Pearson product-moment correlation coefficient (r), an assessment of covariance.

## **Ethical Considerations**

1. All participant will sign a consent form to declare that they are not forced to participate in this study. (Appendix I)
2. The study will be conducted after approval of ethical committee of the Faculty of physical therapy, Cairo University, Egypt.

